**Table 1**

	Screening	Randomization (1 or 2 days after DMEK)	5 day after DMEK	4 ( $\pm$ 2) weeks after DMEK	3 ( $\pm$ 1) months after DMEK	6 ( $\pm$ 1) months after DMEK	9 ( $\pm$ 1) months after DMEK
Informed Consent	X						
Inclusion/Exclusion Criteria	X						
Medical and ophthalmic history	X	X	X	X	X	X	X
Adverse Events		X	X	X	X	X	X
Uncorrected visual acuity (Snellen)	X	X	X	X	X	X	X
Assignment to netarsudil or placebo		X					
Corrected distance visual acuity (Snellen)	X			X	X	X	X
Manifest refraction	X			X	X	X	X
Endothelial cell density (if possible)	X			X	X	X	X
Intraocular pressure	X			X	X	X	X
Ultrasonic pachymetry	X			X	X	X	X

**3.2 Data Analysis and Data Monitoring:** The primary outcome measure is the incidence of clinically significant IOP elevation (defined as IOP  $\geq$  24 mm Hg or a relative increase over the baseline reading of  $\geq$  10 mm Hg). Previous study results conservatively suggest that the rate of IOP elevation will be 20% or greater in the placebo-control arm. Based on the mechanism of action and clinical trial results, we estimate that the relative odds ratio will be 0.25 in the netarsudil study arm. A sample size of 84 per study arm (total = 168) would provide 80% power to detect a statistically significant difference between groups at a 5% significance level (two-sided test). Assuming up to 10% drop out, the required recruitment is 186 study eyes.

Statistical analysis will be conducted on an intent-to-treat basis (i.e. all randomized subjects will be included in the analysis). Data will be analyzed with Statistical Analysis Software (SAS Version 9.4, SAS Institute, Cary, NC) using Kaplan Meier survival analysis and proportional hazards analysis.

**3.3 Data Storage and Confidentiality:** Research data will be stored in a locked cabinet or locked room and on a password protected server to prevent unauthorized access to data. The investigators and research staff will have access to the data. Subject identifiers will be removed and data will be aggregated for publication or presentation of study results.

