### **1.2 Background**

Topical corticosteroids are commonly used to control postoperative ocular inflammation. They are also the mainstay for preventing and treating corneal transplant rejection and for treating ocular conditions involving immune hyper-reactivity. The principal drawbacks include steroid-induced ocular hypertension and steroid-induced glaucoma. The incidence varies with the type of glucocorticoid and its formulation, the dosing frequency, and the treatment duration.

Prednisolone acetate 1% ophthalmic solution is the most commonly used topical corticosteroid in the U.S. Treatment duration ranges from a few weeks, for controlling postoperative inflammation, to years, for preventing cornea transplant rejection. Up to 35% of patients without a prior glaucoma diagnosis and up to 80% with pre-existing glaucoma experience clinically significant post-keratoplasty IOP elevation with long-term topical corticosteroid use. Intraocular pressure elevation is associated with reduced visual acuity and increased risk of transplant failure.

Corneal transplantation offers a unique opportunity to evaluate potential methods for preventing IOP elevation associated with long-term use of topical corticosteroids, without the confounding factors present with immune hyper-reactivity disorders.

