**2.6: Exclusion criteria:**

- A patient exhibiting pre-operative intraocular inflammation.
- A patient with a known sensitivity to any of the ingredients in the study medications
- A patient who has a condition (i.e., UNCONTROLLED systemic disease) or is in a situation which in the investigator's opinion may put the patient at significant risk, may confound the study results, or may interfere significantly with the patient's participation in the study
- A patient with abnormal eyelid function.
- A patient that is exhibiting active corneal ulceration, keratitis, or conjunctivitis, or who has a history of herpetic keratitis.
- A patient who has been diagnosed with uncontrolled glaucoma, prior aqueous shunt or trabeculectomy, or with preoperative IOP > 22 mm Hg in the potential study eye.
- Presence of any ocular disease that would interfere with the evaluation of the study treatment. However, patients with a history of cystoid macular edema, age-related macular degeneration, corneal neovascularization, and other non-interfering comorbidities may be enrolled.
- A patient with a history of non-compliance with using prescribed medication.
- A patient who is concurrently involved in or participated in another randomized clinical trial within 30 days prior to enrollment in this study.
- Patients who are pregnant or planning to become pregnant within the duration of the study

**2.7 Vulnerable Subjects:** No potentially vulnerable subjects will be enrolled because there may be no direct benefit to the patient; rather, important knowledge which may benefit future subjects is being sought. As such, the direct benefit would not outweigh risks for vulnerable populations.

Minors will not be enrolled into this study because the conditions being studied under this protocol are not typical problems for minors. Endothelial keratoplasty is performed to treat endothelial dysfunction, a condition usually seen only in older (>40 years of age) adults.)

Pregnant women will not be enrolled into this study as potential risks and harm to the fetus is unknown.

This study plans to exclude any person who does not speak English as non-English speaking patients are not normally seen at the study site so a translator would not be available to translate the consent form into the patient's native language.

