### **3.0 Methods & Procedures**

#### **3.1 Study procedures and assessments.**

- **Screening and Enrollment:** Prospective subjects will be considered for entry into the study. Subjects meeting the inclusion and exclusion criteria will be informed of the opportunity to participate in the study. Subjects will be entered into the study after providing written informed consent. Each subject will be instructed that if they decide not to participate, they may withdraw at any time.
- **Randomization:** Netarsudil ophthalmic solution 0.02% and placebo eye drops will be dispensed to study subjects in 2.5 ml bottles, identical in appearance. A designated, unmasked, dosing coordinator will apply a coded sticker to each bottle. A computer generated randomization table will be generated. During the routine follow up exam 1 or 2 days after transplantation, the study subject will be randomly assigned to receive netarsudil or AR-13324 placebo (netarsudil vehicle). Both the subject and the investigator will remain masked as to the assigned treatment. If a study participant elects to have both eyes enrolled in the study, the dosing coordinator will automatically assign the second eye to the opposite treatment group from that of the first eye.
- **Study Treatment Regimen:** Subjects will be instructed to instill the assigned eye drop into the study eye once nightly for the 9-month study duration. As standard of care to prevent cornea transplant rejection, subjects will use prednisolone acetate 1% eye drops 4 times daily for the first 3 months, then 3 times daily during month 4, twice daily during month 5, and once daily during months 6 to 9.
- **Study Drug Accountability:** Subjects will be asked to bring back to the clinic all study bottles, both used and un-used. All study drug bottles will be reconciled and recorded.
- **Rescue Medication:** if a study subject develops IOP elevation (a measurement  $\geq 24$  mm Hg or an increase over the screening pre-operative reading of  $\geq 10$  mm Hg), the dosing coordinator will be notified. If the affected eye was assigned to the placebo group, the subject will be offered the opportunity to crossover to the netarsudil group to determine whether that adequately reduces IOP. Depending upon the severity of the IOP increase, the investigator may decide whether it is in the patient's best interest to reduce corticosteroid strength and/or dosing frequency and/or initiate use of approved glaucoma medications.
- **Examinations:**

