- Schedule: Each subject will be examined at screening, 1, 3, 6 and 9 months after endothelial keratoplasty as detailed in Table 1. The examination schedule and procedures are standard of care for endothelial keratoplasty patients.
- Procedures: At 5 day, 1, 3, 6, and 9 month exams, medical and ophthalmic histories will be updated, adverse events will be recorded, and measurements of visual acuity will be made. At 1, 3, 6 and 9 month exams, measurements of manifest refraction, corneal thickness (pachymetry) and intraocular pressure will be made. Corneal endothelial cell density will be measured by specular or confocal microscopy if possible.. A slit lamp examination will be performed to assess the health of the transplant and document any conjunctival or lid hyperemia, stromal inflammation, superficial punctate keratitis, other surface toxicity of the cornea, neovascularization of the cornea, cells or flare in the anterior chamber, or evidence of transplant rejection.
- Records release: Subjects may be asked to sign a records release form in case the subject sees another eye specialist while enrolled in the study. This will allow the investigator to determine if there is a rejection episode or elevated intraocular pressure at examinations made with other physicians. The primary outcome (intraocular pressure) is a routine ophthalmic exam procedure, so the subject may have some exams performed by a local eye doctor if returning to the study site for all exams is too burdensome.
- Unscheduled examinations: Subjects will be instructed to return for extra examinations if they note any problems with the eye or any early signs of a possible rejection episode, such as a change in vision, redness to the eye, increased light sensitivity, burning sensation, or foreign body sensation.
- Study completion: Subjects will be considered to have completed the study after they complete the 9-month examination.
- Subject withdrawal or discontinuation: Each subject may voluntarily discontinue the study at any time they choose. Subjects who cannot complete the study for administrative reasons (e.g., non-compliance, failure to meet visit schedule, etc.) will be discontinued from the study. Discontinued subjects may be replaced. For

subjects withdrawn from the study, the same measurements and assessments should be performed as done at the 9-month exit exam. Adverse events should be followed up until resolution or stabilization of the adverse event.

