Anticipated rare adverse events include retinal detachment, iris synechiae/atrophy, epiretinal membrane, infectious keratitis or conjunctivitis, branch retinal vein occlusion, or endophthalmitis.

Serious Adverse Event: A serious adverse event is one that results in any of the following outcomes: death, a life-threatening adverse event, inpatient hospitalization or prolongation of existing hospitalization, a persistent or significant disability/ incapacity, or a congenital anomaly/birth defect. In the event of a serious adverse event, the investigator will maintain complete documentation and promptly inform the governing Institutional Review Board (IRB) of the serious adverse event within their required reporting period.

Fellow eye: Patients in this population tend to be affected with the eye condition bilaterally, so many of the study subjects may undergo surgery on the fellow eye during study participation.

Routine fellow-eye post-surgical complications will not be transcribed to the eCRF unless the fellow eye is enrolled in the study at the time of the event.

**4.2 Protection Against Risks:** Every effort will be made to minimize any risks or discomforts to study subjects. The investigator will ensure appropriate training of study personnel and monitoring of subjects and will provide appropriate treatment for eye-related adverse events or referral for treatment of non-eye-related adverse events. The subject and or their health insurance plan will be responsible for payment for treatment, counseling or follow up.

A **Data Safety Monitoring Committee (DSMC)** will be chaired by [name], an independent ophthalmologist practicing in Menasha, Wisconsin. The DSMC will review any serious adverse events as they occur. The DSMC will also review the interim data (including adverse events and subject compliance) every 6 months, to determine if any modifications to the original study plan may be warranted. The DSMC meeting minutes and recommendations will be documented and shared with IRBCo, Inc. and with the provider of the investigational product, Aerie Pharmaceuticals.

**4.3 Potential Benefits to the Subjects:** Study subjects may not realize any direct benefit from participation in the research; rather, important knowledge which may benefit future subjects is being sought.

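### Section 3.2 names no terms for the proportional hazards model; adding pre-existing glaucoma, fixed at screening, would be a cheap improvement rather than the repair of an error, and a linear screening-IOP term should not be added

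*Combined protocol and SAP*

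**What the plan says.** - **Analysis (section 3.2).** The analysis is by intention to treat, "using Kaplan Meier survival analysis and proportional hazards analysis". No covariate, stratum or other model term is named there or elsewhere.
- **Randomisation (section 3.1).** "A computer generated randomization table will be generated". No stratification factor is given.
- **Prognosis (section 1.2).** On prolonged steroid drops, the background says: "Up to 35% of patients without a prior glaucoma diagnosis and up to 80% with pre-existing glaucoma experience clinically significant post-keratoplasty IOP elevation".
- **Eligibility (section 2.6).** The glaucoma-related exclusion is "A patient who has been diagnosed with uncontrolled glaucoma, prior aqueous shunt or trabeculectomy, or with preoperative IOP" above 22 mm Hg in the potential study eye. Controlled glaucoma is not on the list, so it is eligible by implication.
- **Data collected (Table 1 and section 3.1).** Ophthalmic history and IOP are both scheduled at screening. Table 1 has no separate glaucoma yes/no item. At the follow-up exams, "medical and ophthalmic histories will be updated".
- **Endpoint (section 3.2).** An event is an IOP of 24 mm Hg or more, or a rise of 10 mm Hg or more over baseline. Section 3.2 does not define baseline. The rescue paragraph in 3.1 uses the same thresholds and refers to "an increase over the screening pre-operative reading of" 10 mm Hg or more.
- **Two eyes (sections 3.1 and 4.1).** If both eyes are enrolled, "the dosing coordinator will automatically assign the second eye to the opposite treatment group from that of the first eye". Section 4.1 expects that "many of the study subjects may undergo surgery on the fellow eye during study participation".

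**The concern.** The protocol itself singles out a strong baseline predictor of the primary event, admits patients who have it and takes the history that would identify it. The planned model then appears to ignore it. In a proportional hazards model with few events, leaving out a strong predictor costs some power, and this trial was sized for 80% with little to spare.

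There is also a practical trap. Because the history is updated at follow-up, a glaucoma covariate added later without a rule could pick up diagnoses made after treatment began. The covariate would then be partly a consequence of the outcome.

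**Working it through.** **1. The plan's own figures.** Inputs from section 3.2: placebo rate 20%, odds ratio 0.25, 84 eyes per arm, two-sided 5%, 80% power, 10% dropout.

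- Netarsudil odds = 0.25 × 0.20/0.80 = 0.0625, so risk = 0.0625/1.0625 = 0.0588.
- Two-proportion normal approximation, unpooled variance: 84.8 per arm, or 85. Arcsine version: 82.1, or 83. The stated 84 is reproduced to within one eye per arm.
- Recruitment: 168/0.9 = 186.7, against 186 stated.

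None of these figures depends on covariate adjustment.

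**2. Events available.** 84 × (0.20 + 0.0588) = 21.7. With treatment and glaucoma in the model, 21.7/2 = about 11 events per term.

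**3. What the background contrast implies.** At face value the odds ratio is (0.80/0.20)/(0.35/0.65) = 7.4. Both percentages are ceilings, so 7.4 serves only as a rough upper marker.

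**4. Power gain from glaucoma, independent eyes.** The documents give no IOP standard deviation, glaucoma prevalence or association between screening IOP and outcome, so the following are assumptions. Screening IOP has mean 15 and SD 3, cut at 22. IOP at 1, 3, 6 and 9 months = 15 + 0.5 × (screening − 15) + constant + glaucoma shift (0, 2, 3 or 4 mm Hg) − treatment shift + error (SD 4, within-eye correlation 0.5). Rates are calibrated to 20% and 5.88%. The test is a Cox likelihood-ratio test with Efron ties, with 8,000 replicates (standard error of a paired power difference 0.1 to 0.3 points).

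| Glaucoma prevalence | Odds ratio | Power, treatment only | Power, + glaucoma | Gain (points) |
|---|---|---|---|---|
| 10% | 1.0 | 81.8 | 81.8 | 0.0 |
| 10% | 2.6 | 80.3 | 80.6 | +0.3 |
| 10% | 4.0 | 81.0 | 82.1 | about +1 |
| 10% | 6.4 | 80.6 | 83.3 | about +2.7 |
| 25% | 2.6 | 80.8 | 82.1 | +1.3 |
| 25% | 4.1 | 81.1 | 83.6 | +2.5 |
| 25% | 6.6 | 80.3 | 84.1 | +3.8 |

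A second simulation, built directly on proportional hazards, included a case with 10% prevalence, a glaucoma hazard ratio of 3.7 and no IOP effect. Power went from 77.4% to 78.6% (+1.2) in a model that also carried a screening-IOP term (about 1,500 replicates).

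**5. Patients with both eyes enrolled.** These runs used one eye per arm, shared glaucoma status, a patient-clustered robust test and 4,000 replicates. They added glaucoma and linear screening IOP together, so they only approximate the glaucoma-only gain. At odds ratios 1.0, 2.6, 6.4 (10% prevalence) and 6.6 (25%), the changes were:

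- 40% of eyes in two-eye patients: −0.2, +0.8, +1.7, +2.3 points.
- 80% of eyes in two-eye patients: 0.0, −0.6, +0.7, +1.1 points.

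If the model is instead stratified by patient and glaucoma status is the same in both eyes, the covariate cancels within each stratum and the gain is nil.

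**6. Why not screening IOP as well.** For screening value s, the event threshold is min(s + 10, 24). Under step 4 the expected follow-up IOP is 7.5 + 0.5s, plus terms that do not depend on s. The distance to the threshold, before those terms, is:

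- s ≤ 14: (s + 10) − (7.5 + 0.5s) = 2.5 + 0.5s
- s ≥ 14: 24 − (7.5 + 0.5s) = 16.5 − 0.5s

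This gives 6.5 at s = 8, 9.5 at s = 14 and 6.5 at s = 20. Risk is V-shaped around 14, close to the assumed mean. Simulated placebo risk was about 30% at 8–10 mm Hg, 14% at 12–16 and 30% at 18–20. Correlation with the event was 0.07 for linear IOP and 0.19 for |IOP − 14|. A linear term alone changed power by −0.1 to +0.3 points.

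**7. Side effects of adjusting.** These were run with both covariates. Null rejection rates were 5.4, 5.6 and 5.3% adjusted against 5.2, 5.2 and 5.3% unadjusted (Monte Carlo standard error about 0.25). The median hazard ratio was 0.24–0.26 adjusted against 0.26–0.27 unadjusted.

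**The case against.** The strongest reply is that this is a preference. The treatment-only analysis is valid, its 5% error rate already allows for chance imbalance in glaucoma, and a sentence excluding covariates would settle the model just as well. That stands, and it is why the point is minor. Such a sentence would, however, forgo whatever gain there is.

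Other objections also stand in whole or part:

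- The 35% and 80% are ceilings for post-keratoplasty patients generally, and section 2.6 removes the more severe glaucoma. Gains above 2.5 points need odds ratios of 6.4 to 6.6, near the face-value 7.4.
- Some of the gain may be slightly inflated test size. Near 80% power, 0.2 to 0.4 points of extra size is worth roughly 0.5 to 1 point of power. The null rates in step 7 are close to 5% but do not exclude this.
- The benefit depends on how paired eyes are analysed, which section 3.2 does not state.

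Three stronger readings are tempting, and the documents do not support them:

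- *The unadjusted result would be biased or invalid.* Treatment is randomised, so it would not be.
- *Screening IOP must be a covariate because the endpoint is defined against it.* Only one of the two criteria is relative to it, and step 6 shows that a linear term can have the wrong shape. Such a term added 4.5 to 6.2 points only if IOP did not regress to the mean at all (slope 1 in place of 0.5), an optimistic bound.
- *The missing terms invite choosing a model after seeing the data.* If an analyst reported the best of four models (none, IOP, glaucoma, both), null runs gave at least one p < 0.05 in 6.2 to 7.4% of trials. That is a worst case; nothing in the documents suggests such a choice is intended.

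**Conclusion.** The point holds as a cheap improvement of minor weight, to consider. The plan's analysis is not in error.

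Adding screening glaucoma status to the primary model would bring 0 to +1.3 power points if glaucoma is weakly to moderately prognostic among enrolled eyes (odds ratio 1.0 to 2.6), about +1.0 to +2.5 at about 4, and at most +3.8 at 6.4 to 6.6. These figures assume independent eyes, 10% or 25% prevalence and the IOP model in step 4. With many two-eye patients the gain is smaller and could be absent.

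That glaucoma is prognostic rests on section 1.2. How strongly it is so in this trial, and how many enrolled eyes have it, cannot be read from the documents. The case against linear screening IOP rests on the assumed regression to the mean.

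**What to change.** Before unmasking, state in section 3.2 that:

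- the primary proportional hazards model contains treatment and pre-existing glaucoma in the study eye (yes/no, from that eye's screening history and not updated afterwards), and no other covariates;
- the primary p-value and hazard ratio come from this model, the hazard ratio being conditional on glaucoma status;
- the unadjusted Kaplan-Meier and log-rank results are supporting.

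Do not enter screening IOP as a single linear term. Add a glaucoma yes/no item to the screening form, or state how it is derived from the recorded history. Settle the method for two eyes of one patient in the same edit, since stratifying by patient would remove the reason for the covariate when both eyes share glaucoma status.

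**Cost.** A few sentences and one item from a history already taken; no visit, sample size or stated figure changes. The downsides are about 11 events per model term, a conditional hazard ratio not directly comparable with the planned odds ratio of 0.25, and possibly no gain if glaucoma is rare or weakly prognostic among enrolled eyes.

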#### **4.0 Risk/Benefit Assessment**

##### **4.1 Risks and Anticipated Adverse Events:**

Risks: This study is considered moderate risk. Netarsudil is an investigational drug - a New Drug Application (NDA) was recently submitted to the U. S. Food and Drug Administration.

A number of complaints and complications are anticipated in patients who have received a cornea transplant, regardless of whether they participate in this study. Therefore, the presence or absence of the following anticipated complaints and complications in the study eye will be recorded on the electronic case report form (eCRF) for each exam rather than on separate adverse event forms.

- Complaints of ocular discomfort: (examples include: eye pain, irritation, burning, itching, scratchy feeling, foreign body sensation, tired/fatigued feeling, achy/tender/sore feeling, pressure sensation, tightness, twinge/twitchy feeling, dry eyes, tearing/watering, eye redness)
- Complaints of visual symptoms or disturbances: (examples include: glare or fluctuating vision, haloes around lights, diplopia, blurry, hazy, cloudy, filmy or out of focus vision, ghosting or shadowing, difficulty reading, difficulty with night driving, floaters, spots in vision, light sensitivity, decreased vision, light reflections from intraocular lens or peripheral iridotomy).
- Increased ptosis (within the first 6 months of surgery)
- Puffy eyelids (within the first 3 months of surgery)
- Delayed resolution of corneal haze or edema (within the first 6 months of surgery)
- Subconjunctival hemorrhage (within the first 3 months of surgery)
- Epithelial defect (within the first month of surgery)
- Folds in the transplant

- Partial graft detachment without further intervention
- Development of capsular haze
- Superficial punctate keratitis
- Pupillary block (within the first 3 months of surgery)

Adverse events: The type, severity, duration and frequency of the following anticipated adverse experiences and any other unanticipated ocular adverse events will be tabulated. If a patient experiences an adverse reaction, appropriate medical treatment will be provided. Examples may include:

- Graft detachment which requires intervention
- Immunologic graft rejection episode
- Graft failure and/or regraft
- Intraocular pressure elevation which requires intervention
- Development of capsular haze which requires intervention
- Iris synechia
- Cystoid macular edema
- Iritis

Anticipated rare adverse events include retinal detachment, iris synechiae/atrophy, epiretinal membrane, infectious keratitis or conjunctivitis, branch retinal vein occlusion, or endophthalmitis.

Serious Adverse Event: A serious adverse event is one that results in any of the following outcomes: death, a life-threatening adverse event, inpatient hospitalization or prolongation of existing hospitalization, a persistent or significant disability/ incapacity, or a congenital anomaly/birth defect. In the event of a serious adverse event, the investigator will maintain complete documentation and promptly inform the governing Institutional Review Board (IRB) of the serious adverse event within their required reporting period.

Fellow eye: Patients in this population tend to be affected with the eye condition bilaterally, so many of the study subjects may undergo surgery on the fellow eye during study participation.

Routine fellow-eye post-surgical complications will not be transcribed to the eCRF unless the fellow eye is enrolled in the study at the time of the event.

**4.2 Protection Against Risks:** Every effort will be made to minimize any risks or discomforts to study subjects. The investigator will ensure appropriate training of study personnel and monitoring of subjects and will provide appropriate treatment for eye-related adverse events or referral for treatment of non-eye-related adverse events. The subject and or their health insurance plan will be responsible for payment for treatment, counseling or follow up.

A **Data Safety Monitoring Committee (DSMC)** will be chaired by [name], an independent ophthalmologist practicing in Menasha, Wisconsin. The DSMC will review any serious adverse events as they occur. The DSMC will also review the interim data (including adverse events and subject compliance) every 6 months, to determine if any modifications to the original study plan may be warranted. The DSMC meeting minutes and recommendations will be documented and shared with IRBCo, Inc. and with the provider of the investigational product, Aerie Pharmaceuticals.

**4.3 Potential Benefits to the Subjects:** Study subjects may not realize any direct benefit from participation in the research; rather, important knowledge which may benefit future subjects is being sought.

**4.4 Study termination:** The study may be prematurely terminated if, in the opinion of the investigator or the Sponsor, there is sufficient reasonable cause. Written notification, documenting the reason for study termination, will be provided to the investigator or Sponsor by the terminating party. Circumstances that may warrant termination include, but are not limited to:

- Determination of unexpected, significant, or unacceptable risk to subjects.
- Insufficient adherence to protocol requirements.
- Data that is not sufficiently complete or evaluable.

- Plans to modify, suspend or discontinue marketing of the Study Product.

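### Section 4.1 leaves ocular discomfort (including redness), superficial punctate keratitis and non-serious non-ocular events out of the adverse event tabulation, and no by-arm summary of them is planned

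*Combined protocol and SAP*

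**What the plan says.** Section 4.1 handles two groups of events differently.

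- **Checklist.** Anticipated complaints and complications in the study eye are noted as present or absent. They "will be recorded on the electronic case report form (eCRF) for each exam rather than on separate adverse event forms". The reason given is that they are expected after a transplant whether or not the patient joins the study.
- **Adverse events.** For a second list, the plan is: "The type, severity, duration and frequency of the following anticipated adverse experiences and any other unanticipated ocular adverse events will be tabulated". That list is introduced as examples. The text does not say that the tabulation is by arm.

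Section 3.1 (Examinations, Procedures) has the slit-lamp examiner "document any conjunctival or lid hyperemia, stromal inflammation, superficial punctate keratitis, other surface toxicity of the cornea", among other findings. It requires no grade and names no summary. The same section says that at the 5-day and later exams "adverse events will be recorded, and measurements of visual acuity will be made", with no restriction to the eye. Table 1 has adverse events recorded at every visit from randomisation on. Section 4.2 foresees events outside the eye, promising "appropriate treatment for eye-related adverse events or referral for treatment of non-eye-related adverse events".

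Section 3.2 defines the intraocular pressure outcome, states intent-to-treat analysis, and names Kaplan-Meier and proportional hazards methods. It describes no safety summary. Under section 4.2 the DSMC reviews interim data, including adverse events, every 6 months, and no table is specified.

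**The concern.** The study drop is described in 4.1 as investigational and is instilled nightly for nine months. Irritation, redness and punctate keratitis can come from surgical recovery or from a drop. Section 3.1 itself names punctate keratitis next to other surface toxicity, so the protocol treats it as a possible sign of toxicity.

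That these findings are expected after surgery is a fair reason not to complete a separate form for each one. It is not a reason to leave them out of a comparison between arms. When a sign has a background rate from surgery, only comparison with randomised controls can separate a drug effect from recovery. This trial has that control: masked, randomised vehicle. Without a planned table, the comparison would be made only if someone later decided to make it.

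The wording about unanticipated ocular events raises a second, smaller issue. Events outside the eye are recorded, but the tabulation sentence does not reach them.

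**Working it through.** The plan gives no figure on this point, and its sample size calculation plays no part. The check is a comparison of texts.

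**1. Which checklist items last the whole study?** The checklist has 12 lines.
- Six have a limit of 1, 3 or 6 months after surgery: ptosis, puffy eyelids, delayed clearing of haze or edema, subconjunctival hemorrhage, epithelial defect and pupillary block.
- The other 12 − 6 = 6 have none: ocular discomfort, visual symptoms, folds in the transplant, partial detachment without intervention, capsular haze and superficial punctate keratitis.

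Ocular discomfort, which names burning and redness, and punctate keratitis are therefore kept off adverse event forms throughout the study.

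**2. Can they enter the tabulation another way?** It has two entry routes.
- *The second list.* None of its 8 examples is discomfort, redness or punctate keratitis, nor is any of the rare events named after it. Because the list is only of examples, this alone is not decisive. Graft detachment and capsular haze do appear there in a form requiring intervention; discomfort and punctate keratitis have no such counterpart.
- *Unanticipated ocular events.* Checklist items are expressly anticipated, so they do not fit.

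Neither route takes them, and the checklist rule keeps them off the forms.

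**3. What of the slit-lamp findings?**

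| Finding (3.1) | Route to the 4.1 tabulation |
|---|---|
| Evidence of rejection | On the second list |
| Cells or flare | Possible, as iritis |
| Conjunctival or lid hyperemia | On neither list; not barred, but not stated |
| Other surface toxicity | Not stated |
| Superficial punctate keratitis | On the checklist, so excluded |

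**4. Non-ocular events.** Recording is unrestricted (3.1, Table 1), but the catch-all in the tabulation sentence is limited to ocular events. Serious events of any kind are documented, reported to the IRB and reviewed by the DSMC (4.1, 4.2). The events left out are the non-serious non-ocular ones.

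**5. Is there a by-arm summary elsewhere?** Section 3.2 has none. The DSMC review might include checklist data, but the text does not say so.

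**6. What can be recovered?** Incidence of checklist items can be, since presence or absence is entered at each exam. Severity and duration are not required for them, so severity would be available only where an examiner chose to note it.

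**The case against.** The strongest reply is that most of the data are captured under masking and randomisation, so a by-arm table can be produced at any time. Section 3.2 is short and gives no summary for visual acuity, endothelial cell density or pachymetry either. The omission therefore looks like brevity. This stands as to weight: nothing suggests an intention to conceal, and incidence is not lost. It does not remove the point, because 4.1 goes beyond silence. It states a rule on what is tabulated, and following that rule excludes these items.

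A reader might infer more than the documents support:

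- *That the slit-lamp findings as a whole escape the safety table.* Rejection is on the tabulated list, cells or flare can enter as iritis, and nothing bars hyperemia from being reported as an unanticipated event.
- *That no one reviews these data during the trial.* The DSMC's remit is interim data including adverse events, which is not confined to adverse event forms. This mitigates the gap, though no table is specified.
- *That the trial loses power to detect surface toxicity.* The documents give no rates for these signs, so any power figure would rest on assumed ones. It would also describe a presence/absence comparison that the existing eCRF data already allow, so it would not measure what the missing sentence costs.
- *That ungraded signs are a design error.* No stated objective needs a grade, and 3.1 lets local eye doctors perform some exams, which makes consistent grading harder.

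**Conclusion.** The point holds as a gap in planned safety reporting. Followed literally, section 4.1 produces an adverse event table without ocular discomfort (including redness), superficial punctate keratitis and non-serious non-ocular events. For hyperemia and other surface toxicity, inclusion is left open. No section plans a by-arm summary of any of these.

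Its weight is moderate. The primary analysis is untouched and incidence can be recovered from the eCRF, but only as an unplanned summary. No numerical size can be given, because the documents state no rates. The conclusion rests on reading the checklist rule and the tabulation sentence as written. It does not assume that netarsudil raises the rate of any of these signs. The correction is worth making because it is specific, cheap and uses a control group already in place.

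**What to change.** **In 4.1, add a by-arm table.** State that the checklist items and the slit-lamp surface signs (hyperemia of the conjunctiva or lids, superficial punctate keratitis, other surface toxicity) will be tabulated by randomised arm and visit, alongside the adverse events.

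**Keep every eye in its randomised arm in the main table.** After an intraocular pressure elevation in a placebo eye, 3.1 says "the subject will be offered the opportunity to crossover to the netarsudil group". Only placebo eyes can cross over. Removing their later exams would select on a post-randomisation outcome while netarsudil eyes with an elevation stayed in, and it would sit badly with the intent-to-treat statement in 3.2. Show placebo eyes' exams after crossover as a supplementary display. At the planning rate of 20%, about 0.20 × 84 = 16.8, or 17, placebo eyes could be offered crossover; how many would accept is not known.

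**Extend the tabulation to all recorded adverse events.** Give non-ocular events in subjects with both eyes enrolled their own line. Section 3.1 has the dosing coordinator "automatically assign the second eye to the opposite treatment group from that of the first eye", so such events cannot be assigned to one arm.

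**Optional.** Add a severity field for hyperemia and punctate keratitis at the 1, 3, 6 and 9 month exams: at most 186 eyes × 4 exams × 2 signs = 1,488 entries. This would need a defined scale that outside examiners can also use.

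**Cost.** One or two extra tables and no new visits. The required changes use data already collected. The reported safety profile may look less favourable.
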